NON-INTERVENTIONAL (NI) STUDY PROTOCOL

Study information

Title	Comparison of Antidepressants in the Real-World: Retrospective Cohort Study Using Big Data
Protocol number	B2061147
Protocol version identifier	Amendment 1
Date	10 February 2021
Active substance	DESVENLAFAZINE (N06AX23)
Medicinal product	Pristiq
Research question and objectives	
Research question: What is the real-world data on antidepressant therapy that can be found in the nationwide claims database in Korea?
 
Primary objectives:
 
1. Explore baseline characteristics and drug utilization patterns of 11 commonly used antidepressant therapy during 90 days of acute treatment phase2. Explore drug utilization patterns such as therapy changes, medication compliance and recurrence relationship, and risk of adverse outcomes during maintenance phase 
Secondary objectives:
 
1. Choice of antidepressants and drug utilization patterns in patients with various comorbidities2. The relationship of non-pharmacologic treatment and discontinuation, medication compliance

PFIZER CONFIDENTIAL

[REDACTED]

	3. Choice of antidepressants by non-psychiatric specialty
Author	PPD [REDACTED], M.D. PPD [REDACTED] [REDACTED], Pfizer Korea PPD [REDACTED] [REDACTED] PPD [REDACTED], MA, PhD PPD [REDACTED] [REDACTED] [REDACTED]

[figure not shown]
PFIZER CONFIDENTIAL

2. LIST OF ABBREVIATIONS

Abbreviation	Definition
HIRA	Health Insurance and Review Assessment
MPR	Medication Possession Ratio
ICD-10	International Classification of Diseases 10 th revision
KCD-7	Korean Standard Classification of Diseases 7 th revision
MDD	Major Depressive Disorder
MCI	Mild cognitive impairment
COPD	Chronic Obstructive Pulmonary Disease
CAD	Coronary Artery Disease
CVA	Cerebrovascular Accident
CBT	Cognitive Behavioral Therapy
SSRI	Selective serotonin reuptake inhibitor
SNRI	Serotonin–norepinephrine reuptake inhibitor
NHI	National Health Insurance
AD	Antidepressants

PFIZER CONFIDENTIAL

[figure not shown]

4. ABSTRACT

Title: Comparison of Antidepressants in the Real-World: Retrospective Cohort Study Using Big Data

Rationale and background

While there are many antidepressants from which physicians can select based on efficacy and tolerability profile, evidence on effectiveness and safety outcomes of new antidepressants in real clinical practice among Korean MDD population is limited. Hence, the aim of this study is to investigate medication utilization pattern and risk of adverse outcomes among commonly used antidepressants by using nationwide claims database, in order to assess overall clinical benefit of antidepressant therapy in real-world practice.

Research question and objectives

Research question: What is the real-world data on antidepressant therapy that can be found in the nationwide claims database in Korea?

Primary objectives:

1. Explore baseline characteristics and drug utilization patterns of 11 commonly used antidepressant therapy during 90 days of acute treatment phase
2. Explore drug utilization patterns such as therapy changes, medication compliance and recurrence relationship, and risk of adverse outcomes during maintenance phase

Secondary objectives:

1. Choice of antidepressants and drug utilization patterns in patients with various comorbidities
2. The relationship of non-pharmacologic treatment and discontinuation, medication compliance
3. Choice of antidepressants by non-psychiatric specialty

Study design: Retrospective cohort study

Population:

Subjects who newly initiated antidepressant therapies between Jan 01, 2017 to Jun 30, 2019 in the Health Insurance and Review Assessment (HIRA) database

**Index date is the first prescription date of study drugs, including SSRIs, SNRIs, and other ADs during the intake period (Jan 01, 2017 to Dec 31, 2019)*

Variables – include exposures, outcomes, and key co-variates

Exposure: The exposure to the following will be considered:

1. SSRIs
2. SNRIs
3. Other ADs (including but not limited to mirtazapine, vortioxetine)

Outcome variables: the following will be assessed:

1. Outcomes related to depression
 - AD usage pattern (prescription proportion, dosage and length of treatment, switching, combination, augmentation, discontinuation), compliance, recurrence
2. Adverse outcomes
 - Hyponatremia, GI bleeding, fractures, falls, risk of intracranial hemorrhage, attempted suicide/self-harm, myocardial infarction, epilepsy/seizures, stroke/transient ischemic stroke

Key-Covariates: Variables, including but not limited to, will be age, sex, region, Charlson comorbidity index, psychiatric comorbidities, hospital admission

Data sources

HIRA database from January 01, 2016 to December 31, 2019 will be used for the analysis. It contains the data of universal health insurance system in Korea, wherein patient demographic information, inpatient and outpatient service use, and pharmacy dispensing claims can be obtained.

[figure not shown]
Study size

The study size will be determined based on the HIRA disease statistics, diagnosis code, inclusion and exclusion criteria, and study period. A previous study was conducted using the HIRA data from January 1, 2011 to December 31, 2015, during which 752,190 patients were identified to have been newly prescribed antidepressants with diagnosis of depressive disorder.

Data analysis

Patients will be matched on demographic and clinical characteristics. All outcome variables will be summarized descriptively through the tabular and graphical display of mean values, medians, ranges and standard deviations of continuous variables of interest and frequency distributions of categorical variables. Safety outcomes of treatments will be estimated from time-to-event models. The 95% confidence intervals for the estimates will be calculated and $p<0.05$ will be considered significant. All analyses will be carried out using SAS version 9.4. Analysis and reporting will be compliant with Strengthening the Reporting of Observational Studies in Epidemiology (STROBE) recommendations.

[figure not shown]
PFIZER CONFIDENTIAL

5. AMENDMENTS AND UPDATES

Amendment number	Date	Protocol section(s) changed	Summary of amendment(s)	Reason
Ammendment 1	10Feb2021	2. 3. 4. 6. 9.2 9.4 9.5 9.6 9.8 9.9 12. Figure 1. Table 2. Table 3.	NHIS changed to HIRA. Name and degree of NISL changed. Population, data sources, study size amended to describe HIRA. Database selection period extended to end in 2019. Outcome variables related to depression added. Planned dates for start and end of data collection, interim report, and final study report amended. Population amended to describe HIRA. Database selection period extended to end in 2019. Data sources amended to describe HIRA. Study size amended to describe HIRA. Data management amened to describe HIRA. Database name changed to HIRA. Database name changed to HIRA. Typo corrected. Intake and follow-up period extended to end in 2019. Drug Main Ingredient Codes source changed to HIRA. Data source changed to HIRA.	Correction according to database change Correction according to NISL change Correction according to database change and addition of description of results variable Correction according to database change. Correction of typo Correction according to database change. Correction according to database change. Correction according to database change.

PFIZER CONFIDENTIAL

6. MILESTONES

Milestone	Planned date
Completion of feasibility assessment	28 Jun 2019
Start of data collection	Mar 2021
End of data collection	Jun 2021
Interim report 1	Dec 2021
Final study report	Dec 2022

7. RATIONALE AND BACKGROUND

Major depressive disorder (MDD) is a prevalent disorder, causing great disability in affected individuals.¹⁻³ Its lifetime prevalence is estimated at 6.7% in Korea, and has continued to increase gradually since 2006.⁴ The approximate economic cost of MDD in 2005 was at \$4.5 billion, with indirect cost of \$2.96 billion due to loss of work productivity.⁵

Current guidelines recommend antidepressants like selective serotonin reuptake inhibitors (SSRIs) and selective serotonin norepinephrine reuptake inhibitors (SNRIs) as first-line pharmacotherapy for the management of MDD.⁶⁻⁷ The antidepressant effect not only reduces depressive symptoms but also contributes to patient's overall functional improvement.⁸ Despite plenty of available evidences on antidepressant therapy, Sequenced Treatment Alternatives to Relieve Depression (STAR*D) study showed that only about 30% of patients achieve remission with first-line treatment.⁹ In addition, those patients switching antidepressants compared to those initiating or maintaining first-line antidepressant therapy have different patient characteristics in terms of severity of depressive symptoms, anxiety, worse health-related quality of life, functional impairment.¹⁰ Non-adherence rates are high in MDD, which can lead to suboptimal treatment outcomes.¹¹

While there are many antidepressants from which physicians can select based on efficacy and tolerability profile, evidence on effectiveness and safety outcomes of new

antidepressants in real clinical practice among Korean MDD population is limited. Ahn *et al.* (2011) reported that antidepressant adherence among the Korean patients with MDD is less than 50% and recurrence and deterioration of MDD occurs due to the low adherence in Korea.¹² In addition, it is uncertain how patients are being properly managed with index medications and the proportion of switching, combination, and augmentation therapy during both acute and maintenance phases. And medication adherence and persistence rates are clinically important as they can have a major impact on the outcomes such as recurrence and recovery from depressive symptoms.

Therefore, the aim of this study is to investigate medication utilization pattern and risk of adverse outcomes among commonly used antidepressants by using nationwide claims database, in order to assess overall clinical benefit of antidepressant therapy in real-world practice.

8. RESEARCH QUESTION AND OBJECTIVES

Research question: What is the real-world data on antidepressant therapy that can be found in the nationwide claims database in Korea?

Primary objectives:

- Explore baseline characteristics and drug utilization patterns of 11 commonly used antidepressant therapy during 90 days of acute treatment phase
 - o Top 11 commonly used antidepressants according to local market data are as follows:
 - Escitalopram, paroxetine, fluoxetine, mirtazapine, duloxetine, sertraline, venlafaxine, tianeptine, vortioxetine, desvenlafaxine, bupropion
 - o Proportion of antidepressants prescribed by sex, age (≤ 20 , 21-64, ≥ 65), sex and age combined
 - o Initial doses used, average daily doses of each antidepressants
 - o Average length of treatment with index medication before therapy change occurs (switching, combination, augmentation, discontinuation)

- Adherence and persistence measured by medication possession ratio during first 90 days of treatment period
- Explore drug utilization patterns such as therapy changes, medication compliance and recurrence relationship, and risk of adverse outcomes during maintenance phase
 - The choice of antidepressant, average length of new treatment maintenance, average number of co-administered medications (e.g., atypical antipsychotics, mood stabilizer, thyroid hormone, psychostimulant) when following changes occur from initial monotherapy:
 - Switching
 - Combination
 - Augmentation
 - Medication compliance and recurrence
 - Compliance measured as adherence and persistence
 - Recurrence
 - Relationship between recurrence and compliance
 - Risk of adverse outcomes measurement between individual ADs that are well known to be treatment-related (e.g., hyponatremia, GI bleeding, fractures, falls, risk of intracranial hemorrhage, attempted suicide/self-harm, myocardial infarction, epilepsy/seizures, stroke/transient ischemic stroke)

Secondary objectives:

1. Choice of antidepressants and drug utilization patterns in patients with various comorbidities
 - Psychiatric comorbidities
 - Mild cognitive impairment (MCI)
2. The relationship of non-pharmacologic treatment and discontinuation, medication compliance
 - Non-pharmacologic treatments may include: cognitive behavioral therapy (CBT),

frequency of physician visit during acute and maintenance phase of treatment

- Frequency of visit during the first 3 months of acute phase and its relationship to treatment maintenance at 4, 5, 6, 7, 8, 9 month time points and discontinuation rate

3. Choice of antidepressants by non-psychiatric specialty

- o Rheumatology, cardiology, pulmonology, infectious diseases, nephrology, endocrinology and metabolism, gastroenterology, rehabilitative medicine, neurology, neurosurgery, urology, otorhinolaryngology, gynecology & obstetrics, etc.

9. RESEARCH METHODS

9.1. Study design

Using a retrospective cohort design, this study will evaluate treatment utilization pattern, medication compliance, incidence of recurrence, risk of adverse outcomes of antidepressant therapy, choice of therapy in various comorbidities, and choice of therapy in other specialty that are recorded in national health insurance database.

[figure not shown]

Figure 1. Study design scheme

9.2. Setting

Population

Subjects who newly initiated antidepressant therapies between Jan 01, 2017 to Jun 30, 2019 in the HIRA database

* Index date is the first prescription date of study drugs, including SSRIs, SNRIs, and other ADs during the intake period (Jan 01, 2017 to Dec 31, 2019).

9.2.1. Inclusion criteria

Patients must meet all of the following inclusion criteria to be eligible for inclusion in the study:

1. Patients aged 18 years or older on the index date
2. Patients who had at least one inpatient claim or two outpatient claims in the intake period with any of the following diagnosis codes

Table 1. Diagnosis codes for inclusion

KCD-7 Code1)	Description
F06.3	Organic mood[affective] disorders
F32*	Depressive episode
F33*	Recurrent depressive disorder
F34.1	Neurotic depression
F38.1	Other recurrent mood[affective] disorders
F41.2	Mixed anxiety and depressive disorder

[figure not shown]
[figure not shown]
1) KCD-7 = Korean version of ICD-10

3. Patients prescribed any of the following antidepressant during intake period (from January 1, 2017 to June 30, 2019)

Table 2. Study Drug List

Active Ingredient	Dosage	HIRA Drug Main Ingredient Codes
Escitalopram	5mg	474801ATB
	10mg	474802ATB
	20mg	474803ATB
	15mg	474804ATB
	10mg	521101ATD
	20mg	521102ATD
Paroxetine	10mg	209301ATB
	20mg	209302ATB
	12.5mg	209304ATR
	25mg	209305ATR
Fluoxetine	10mg	161501ACH
	10mg	161501ATB
	20mg	161502ACH
	20mg	161502ATB
	20mg	161502ATD

PFIZER CONFIDENTIAL

Mirtazapine	15mg 15mg 30mg 30mg 7.5mg 7.5mg	196201ATB 196201ATD 196202ATB 196202ATD 196204ATB 196204ATD
Duloxetine	30mg 30mg 60mg 60mg	495501ACE 495501ATE 495502ACE 495502ATE
Sertraline	50mg 0.1g	227001ATB 227002ATB
Venlafaxine	75mg 37.5mg	247502ACR 247504ACR
Tianeptine	12.5mg	229601ATB
Vortioxetine	5mg 10mg 15mg 20mg	628501ATB 628502ATB 628503ATB 628504ATB
Desvenlafaxine	50mg 100mg	626401ATR 626402ATR
Bupropion	0.1g 0.15g 0.3g	428101ATB 428102ATR 428103ATR

9.2.2. Exclusion criteria

Patients meeting any of the following criteria will not be included in the study:

1. Patients with a claim of diagnosis codes in Table 1 during the 12 month pre-index period
2. Patients with a claim of prescription in Table 2 during the 12 month pre-index period
3. Patient who had a claim as a beneficiary of Medical Aid program (Korean Medicaid program with free or minimum copay)
4. Patients who are hospitalized at the index date
5. Patients who are under hospice care (procedure codes WG*-WO*)

9.3. Variables

Table 3. List of Variable Categories

Variable	Role	Data Source	Operational Definition
SSRIs	Exposure	HIRA Database	Prescription claims with a HIRA Drug Main Ingredient code for the following drugs defined in Table 2 will be used individually for each drug: Escitalopram, paroxetine, fluoxetine, sertraline
SNRIs	Exposure	HIRA Database	Prescription claims with a HIRA Drug Main Ingredient code for the following drugs defined in Table 2 will be used individually for each drug: Duloxetine, venlafaxine, desvenlafaxine
Other ADs	Exposure	HIRA Database	Prescription claims with a HIRA Drug Main Ingredient code for the following drugs defined in Table 2 will be used individually for each drug: Mirtazapine, tianeptine, vortioxetine, bupropion
Proportion of Antidepressants	Primary outcome	HIRA Database	For each of 11 study drugs, the following proportions will be calculated 1) Proportion out of total prescriptions in the first 90 days from the index date (acute treatment phase) 2) Proportion out of each gender in the first 90 days from the index date (acute treatment phase) 3) Proportion out of three age groups (≤ 20 , 21-64, ≥ 65) in the first 90 days from the index date (acute treatment phase)

PFIZER CONFIDENTIAL

			
treatment phase)
 
4) Proportion out of 6 subgroups generated by 2 genders and 3 age groups in the first 90 days from the index date (acute treatment phase)

Dosage	Primary outcome	HIRA Database	
For each of 11 study drugs, the following dosages will be calculated
 
 1) Initial dosage at the index date 2) The average dosage during the first 90 day period from the index date (acute treatment phase)
Persistence	Primary outcome	HIRA Database	
For each of 11 study drugs, the average length of treatment on the index drug (allowing 14 day permissible gap) will be calculated
 
 - Switching, combination, augmentation, discontinuation will terminate the persistent period
Discontinuation	Primary outcome	HIRA Database	
For each of 11 study drugs chosen as index drug, the percentage of discontinuation in the first 90 days from the index date (acute treatment phase) will be measured (allowing 14 day permissible gap)

Adherence	Primary outcome	HIRA Database	
For each of 11 study drugs chosen as index drug, adherence will be measured by MPR during the first 90 days from the index date (acute treatment phase)
 
* MPR = (Days of medication possession from the prescriptions filled in the 90 days) / (90 days + extra days of drug supply from the last prescription fill during the 90 days)
 
** For those period with any identified adverse outcome such as GI bleeding will be considered as

			non-adherent period
Drug utilization pattern in acute phase	Secondary outcome	HIRA Database	
During the first 90 day period starting from the index date, the following types of drug utilization pattern is recorded
 
 - monotherapy (kept on the index medication) - switching (switched to other antidepressant) - combination (adding other antidepressant) - augmentation (adding other non-AD drug such as antipsychotic)
Drug utilization pattern in maintenance phase	Secondary outcome	HIRA Database	
During the second 90 day period (91 ~ 180 days) starting from the index date, the following types of drug utilization pattern is recorded
 
 - choice of antidepressant - monotherapy (kept on the same medication) - switching (switched to other antidepressant) - combination (adding other antidepressant) - augmentation (adding other non-AD drug such as antipsychotic)
Recurrence	Primary outcome	HIRA Database	
Recurrence was operationally defined as either one of the following was satisfied:
 
 1) inpatient episode with a diagnosis code in Table 1 2) emergency room visit with a diagnosis code in Table 1 3) suicide attempt identified by the following KCD-7 codes: 
T40 Poisoning by narcotics and psychodysleptics [hallucinogens] T41 Poisoning by anaesthetics and

PFIZER CONFIDENTIAL

			
therapeutic gases
 
T42 Poisoning by antiepileptic, sedative-hypnotic and antiparkinsonism drugs
 
T43 Poisoning by psychotropic drugs, not elsewhere classified
 
T54 Toxic effect of corrosive substances
 
T60 Toxic effect of pesticides
 
X60-X84 intentional self harm

Adverse outcomes	Primary outcome	HIRA Database	
The following known treatment related outcomes will be operationally defined by KCD-7 diagnosis codes and/or NHI procedure codes in medical claims
 
 - GI bleeding I850, I883, K2211, K226, K228, K250, K252, K254, K256, K260, K262, K264, K266, K270, K272, K274, K276, K280, K282, K284, K286, K290, K3181, K5521, K625, K920, K921, K922 - Fractures S02, S12, S22, S32, S42, S52, S62, S72, S82, S92, T02, T08, T10, T12, T14.2 - Falls W00-W19 - Intracranial hemorrhage I60, I61, I62, I690, I691, I692, S064, S065, S066, S068 - Suicide attempt, self-harm T40 Poisoning by narcotics and psychodysleptics [hallucinogens] T41 Poisoning by anaesthetics and therapeutic gases T42 Poisoning by antiepileptic, sedative-hypnotic and antiparkinsonism drugs T43 Poisoning by psychotropic drugs, not elsewhere classified T54 Toxic effect of corrosive substances T60 Toxic effect of pesticides X60-X84 intentional self-harm - Myocardial infarction I21.9, I21.4, I21.0, I21.1, I21.2, I21.3, I22.0A, I22.0B, I22.0C, I22.8A,

PFIZER CONFIDENTIAL

			
I22.8B, I22.8C, I22.8D, I22.8E, I22.8F, I22.8G, I22.8H, I22.8I, I22.8, I22.9, I22.1A, I22.1B, I22.1C
 
 - Epilepsy/seizures G40.XX - Stroke 
 - Transient ischemic attack G459, I63, I693 - Hemorrhagic stroke I60, I61, I62, I690, I691, I692 - Ischemic stroke I63 
[NOTE] Hospitalization and CT or MRI codes such as brain CT or MRI procedure code for ischemic stroke and hemorrhagic stroke, or any CT or MRI for systemic embolism are also required for identification.
 
 * Brain CT HA441, HA451, HA461, HA471, HA851 * Brain MRI HE101, HE102, HE135, HE201, HE202, HE235, HE301, HE302, HE401, HE402, HE501, HE502, HE535 * Any CT or MRI or CT HA401-HA416, HA424, HA425, HA434, HA435, HA443-HA449, HA453, HA456-HA459, HA463-HA469, HA473-HA479, HA496, HA497, HA801, HA805, HA809, HA813, HA834, HA835, HA853, HA856, HA857-HA859, S852 * MRI HE103-HE142, HE203-HE234, HE236-HE241, HE303-HE334, HE403-HE434, HE430-HE434, HE503-HE534, HE536-HE541, HF101, HF102, HF104-HF107, HF201, HF202, HF305, HF306 
 - Hyponatremia 
 - will be identified by
--	--	--	---

			prescription codes for vasopressin receptor antagonists such as tolvaptan (drug code=616501ATB)
Comorbidities	Covariates	HIRA Database	
The following comorbidities which may affect the drug utilization patterns of antidepressants will be operationally defined using KCD-7 diagnosis codes in medical claims
 
 - Psychiatric comorbidities: panic disorder (F41.0), bipolar disorder (F31), PTSD (F43.1), acute stress (F43.0), personality disorder (F60-69), GAD (generalized anxiety disorder) (F41.1), adjustment disorder (F43.2), sleep disorder ((F51), g470, f108), dementia (F00-F03, G30), OCD (obsessive compulsive disorder) ((F42), F429, F605, F428)), substance related disorders (F10-19), schizophrenia (F20-29), eating disorder (F50), sexual dysfunction (F52), mental retardation (F70-F79), developmental disorder (F80-F89), somatoform disorder F45, eating disorder F50 - Mild cognitive impairment (MCI): diagnosis code F06.7 along with a procedure code for neurocognitive function test FB001-FB060* - Charlson Comorbidity Index (CCI)
Non-pharmacologic treatments	Covariates	HIRA Database	The following non-pharmacologic treatments which may affect antidepressant adherence and persistence/discontinuation will be

			
defined using NHI procedure codes* in medical claims
 
 - Individual psychotherapy** NN012 intensive analytic NN013 intensive - Group psychotherapy NN021 general NN022 analytic NN023 psychodrama - Family psychotherapy NN031 individual NN032 group NN040 occupational or recreation therapy NN050 narcotherapy - Electroconvulsive therapy NN071 simple ETC NN072 modified ETC - Continuous sleep treatment NN081 electro sleep treatment NN082 drug induced sleep treatment NN083 sleep treatment with anesthesia NN090 psychiatric rehabilitation NN100 psychiatric emergency treatment - Psychiatric social work NN111 individual history taking NN112 social work guidance NN113 social investigation NN114 home visiting 
* Since January 2018, new code system was employed for psychotherapy and expert advisor consensus will be used to align the new codes to the codes above NN001-NN005 individual psychotherapy NN061 Cognitive Behavioral Therapy-Individual NN062 Cognitive Behavioral Therapy-Group ** NN011 supportive was excluded since it is more of a routine code used for majority of patients according to Ahn et al.

--	--	--	--

			(2012) ¹³
Patient demographics and provider characteristics	Covariates	HIRA Database	The following patient demographics and provider characteristics will be defined using medical claims 
- Age- Gender- Region of provider- Specialty of provider- Class of clinic/hospital
Number of visits	Covariates	HIRA Database	Number of provider visits will be calculated from medical claims 
- Inpatients visits- Outpatient visits- Emergency room visits

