5.1 EFFICACY/EFFECTIVENESS ENDPOINT(S)

Medication compliance (persistence, discontinuation, adherence) along with recurrence are main primary efficacy endpoints and they are defined as follows:

1. MPR (medication possession ratio)
For each of 11 study drugs, the MPR will be calculated by (Days of medication possession from the prescriptions filled in the 180 days) / (180 days + extra days of drug supply from the last prescription fill during the 180 days)
2. Persistence
For each of 11 study drugs, the average length of treatment on the index drug during the first 180 day period (allowing 14 day permissible gap) will be

PFIZER CONFIDENTIAL

calculated. Switching, combination, augmentation, discontinuation will terminate the persistent period.

3. Discontinuation

For each of 11 study drugs chosen as index drug, the percentage of discontinuation in the first 90 days from the index date (acute treatment phase) will be measured (allowing 14 day permissible gap)

4. Adherence

For each of 11 study drugs chosen as index drug, adherence will be measured by MPR and persistence during the first 90 day and 180 day from the index date, respectively (acute treatment phase). MPR ≥ 0.75 and persistence ≥ 90 will be considered as adherence.

* For those period with any identified adverse outcome such as GI bleeding will be considered as a non-adherent period.

5. Recurrence

Recurrence during the acute treatment phase was operationally defined as either one of the following being satisfied:

- 1) Inpatient episode with a diagnosis code in Table 1
- 2) Inpatient episodes via the department of psychiatry or emergency medicine
- 3) Inpatient episode via nursing hospital
- 4) Emergency room visit with a diagnosis code in Table 1
- 5) Suicide attempt identified by the following KCD-7 codes:
 - T40 Poisoning by narcotics and psychodysleptics [hallucinogens]
 - T41 Poisoning by anaesthetics and therapeutic gases
 - T42 Poisoning by antiepileptic, sedative-hypnotic and antiparkinsonism drugs
 - T43 Poisoning by psychotropic drugs, not elsewhere classified
 - T54 Toxic effect of corrosive substances
 - T60 Toxic effect of pesticides
 - X60-X84 intentional self harm
- 6) Augmentation of the following non-AD drugs
 - Antipsychotic: amisulpride, aripiprazole, olanzapine, quetiapine, risperidone, perphenazine
 - Anticonvulsant: carbamazepine, valproic acid, lamotrigine
 - Mood stabilizer: lithium
 - Anxiolytic: buspirone
 - Thyroid hormone: levothyroxine, liothyronine

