Recurrence after the acute treatment phase was operationally defined as either one of the following being satisfied:

- 1) ~6) the same as above
- 7) AD prescription after 30 days of drug holiday

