7.2.2 Study Drug Analysis in Maintenance Phase

- To understand the top 11 antidepressants usage among the Korean patients with depression in maintenance treatment phase
- Primary analysis
- Endpoints:
 - Choice of study drug
 - Average length of new treatment maintenance
 - Average number of co-medications (e.g., atypical antipsychotics, mood stabilizer, thyroid hormone, psychostimulant) when following changes occur from initial monotherapy: switching, combination, augmentation
 - Medication compliance (adherence, discontinuation, and persistence)
 - Recurrence by each antidepressant, by compliance
 - Risk of adverse events
- Population: patients from the acute treatment phase who started maintenance treatment (after 90 days from the index date)
- Significance on continuous variables will be tested by ANOVA (if equal variance condition satisfied) or Kruskal-Wallis H test (otherwise). Provider specialty and other patient characteristics will be used to fit antidepressant choice by multivariate logistic regression analysis of each study drug choice.
- Covariates: antidepressant class covariates such as SSRIs, SNRIs, and other ADs will be used as grouping variables.
- Missing values will be dropped from the analysis
- The role of this analysis is to provide information on study antidepressants in the maintenance phase of drug therapy for Korean patients with depression.

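### Patients who switch before day 90 are scored non-adherent even when another study antidepressant covers every day, and that score is the exposure in the recurrence-by-compliance analysis

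*Protocol*

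**What the plan says.** Protocol 9.3, Table 3, measures adherence by index drug, over the first 90 days: "For each of 11 study drugs chosen as index drug, adherence will be measured by MPR". It gives no cut-off. Its MPR numerator is "Days of medication possession from the prescriptions filled in the 90 days", which does not name the drug. Persistence in the same table is the length of treatment on the index drug with a 14-day gap allowed, and "Switching, combination, augmentation, discontinuation will terminate the persistent period".

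SAP 5.1 keeps the index-drug persistence and its stopping rule (item 2), extends the MPR formula to 180 days (item 1), and adds a binary rule in item 4: "MPR ≥ 0.75 and persistence ≥ 90 will be considered as adherence". Item 4 pairs MPR with 90 days and persistence with 180 days, whereas item 1 gives MPR over 180 days.

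The objectives (Protocol 8, SAP 2.2) define compliance as adherence and persistence, and list "Relationship between recurrence and compliance" under the second primary objective. SAP 7.2.2, labelled a primary analysis, has the endpoint "Recurrence by each antidepressant, by compliance" and includes patients who started maintenance treatment after day 90. Switching is recorded only as a category of the drug utilization pattern, a secondary outcome.

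**The concern.** Index-drug persistence is a sensible measure of how long each of the 11 drugs is kept. The difficulty is its reuse as compliance in a different question. Protocol 7 motivates the study by low adherence to antidepressants and the recurrence that follows; it does not speak of loyalty to the first drug. The same section says that patients who switch differ from those who start or stay on a first-line drug in symptom severity, anxiety, quality of life and function.

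Under the SAP rule, early switchers who take every dose of the new drug sit in the same group as patients who stopped taking medication. A difference in recurrence between compliance groups would then mix the effect of not taking treatment with whatever separates switchers from non-switchers. Nothing planned separates the two. The propensity-score methods in SAP 7.1 are for comparing antidepressants and balance pre-index measures. Switching happens after the index date and is not among the Table 3 covariates. No sensitivity analysis addresses it.

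**Working it through.** The documents give no sample size, effect or rate for this analysis, so there is no planned figure to reproduce.

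**Step 1: apply the SAP rule to a fully covered switcher.** The patient switches on day d without a gap and has an antidepressant every day. Index-drug persistence is d. If MPR counts the index drug only, MPR = min(d, W)/W for window W, with no surplus supply. If MPR counts any antidepressant, MPR = 1.00.

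| Switch day | Index MPR, 90 days | Index MPR, 180 days | Persistence ≥ 90? |
|---|---|---|---|
| 30 | 30/90 = 0.33 | 30/180 = 0.17 | no |
| 60 | 0.67 | 0.33 | no |
| 89 | 0.99 | 0.49 | no |
| 100 | 1.00 | 0.56 | yes |
| 134 | 1.00 | 0.744 | yes |
| 135 | 1.00 | 0.750 | yes |

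A switch before day 90 fails on persistence alone, whichever way MPR is read. If MPR is index-only over 180 days, failure extends to any switch before day 135 (0.75 × 180 = 135). If MPR is read over 90 days or for any antidepressant, a switch from day 90 on passes.

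**Step 2: effect on recurrence by compliance.** Assumptions, none from the documents: a fraction s switches before day 90 and is fully covered; a fraction c of non-switchers is compliant; recurrence is r in non-switchers and k × r in switchers; taking medication has no effect.

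- Scored compliant: risk r.
- Scored non-compliant: risk r × [s·k + (1−s)(1−c)] / [s + (1−s)(1−c)].
- The ratio is the bracketed fraction; r cancels.

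With s = 0.20, c = 0.5, k = 2, r = 10%: (0.20 × 20% + 0.40 × 10%) / 0.60 = 13.3% against 10.0%, a ratio of 1.33. With k = 1 it is 0.60/0.60 = 1.00.

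| s (c = 0.5) | k = 1.5 | k = 2 |
|---|---|---|
| 10% | 1.09 | 1.18 |
| 20% | 1.17 | 1.33 |
| 30% | 1.23 | 1.46 |

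Over s = 10–30% and c = 40–70%, the ratio is 1.08–1.29 for k = 1.5, 1.16–1.59 for k = 2 and 1.31–2.18 for k = 3. With 10,000 patients and r = 10%, the 1.33 case gives p < 0.05 with probability above 0.99 (two-sided test assumed).

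**Step 3: an any-antidepressant measure, same example.** All switchers are now compliant. Compliant: (0.40 × 10% + 0.20 × 20%) / 0.60 = 13.3%. Non-compliant: 10.0%. Ratio 0.75. If instead half of switchers were compliant, each group would hold 0.40 non-switchers and 0.10 switchers, with risk (0.40 × 10% + 0.10 × 20%) / 0.50 = 12% in both, a ratio of 1.00. So this measure is unbiased without stratification only if switchers and non-switchers are equally compliant.

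**Step 4: stratify by switching.** Among non-switchers it is 10% against 10%, ratio 1.00. In this example the switcher stratum has no contrast, because all switchers are compliant. Stratification is what removes the bias; the any-antidepressant definition makes the switcher stratum interpretable when its members vary in compliance.

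**The case against.** The strongest reply is that the analysis is exploratory (the objectives say explore, and SAP 3 lists no hypotheses) and that staying on the first drug is a legitimate descriptive exposure. That stands for the by-drug tables. It does not stand for a primary objective phrased as a relationship between recurrence and compliance, whose rationale is antidepressant adherence in general.

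A reader might infer several stronger claims that the documents do not support:

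- **That every switcher is scored non-compliant.** A switch from day 90 (or from day 135 under the 180-day index-only reading) can be scored adherent. The Protocol row has no cut-off at all; the split comes from the SAP.
- **That MPR is explicitly index-only.** The formula names no drug, and item 1 of SAP 5.1 refers to the study drugs without calling them index drugs. The index-only reading comes from the lead-in to Adherence. The 0.17 and the day-135 limit depend on it and on the 180-day window; the day-90 limit does not.
- **That non-compliance will look harmful.** The documents give no switching rate and no recurrence risk for switchers. Protocol 7 says that they differ in severity and other characteristics, not that most switched because the first drug failed. With equal risk no spurious relationship arises; with lower risk the ratio falls below 1.
- **That recurrence item 7, "AD prescription after 30 days of drug holiday", shows compliance was meant across all antidepressants.** It defines the outcome and settles nothing about the exposure.
- **That an any-antidepressant MPR alone repairs the analysis.** Step 3 shows an error of the same proportion in the other direction (1/0.75 = 1.33). Replacing MPR while keeping index-drug persistence would leave every pre-day-90 switcher non-adherent.

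**Conclusion.** The point holds in a limited form. The misclassification of pre-day-90 switchers follows directly from SAP 5.1 items 2 and 4 and needs no assumption about MPR. Its consequence for recurrence by compliance is conditional: it can create or distort a relationship if switchers have a different recurrence risk, which Protocol 7 makes plausible but does not quantify. The ratio of 1.33 rests on assumed inputs (20% early switching, all fully covered; twice the risk; half of non-switchers compliant; no true effect) and is an illustration, not a prediction. The by-drug adherence and persistence tables are not affected. This is a cheap improvement to one component of a primary objective.

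**What to change.** Keep the index-drug MPR, persistence and adherence for the by-drug tables. For recurrence by compliance in SAP 7.2.2:

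1. Report results stratified by, or adjusted for, switching in the acute phase.
2. Define both MPR and persistence on any Table 2 antidepressant: count overlapping days once, treat a switch to another Table 2 drug as continued treatment, and end the compliance window before recurrence starts to be counted. State which window applies, since SAP 5.1 items 1 and 4 differ.
3. Do not report the any-antidepressant result unstratified on its own.

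The cost is one extra derived compliance measure from prescriptions that the study already uses, plus SAP wording. The downside is that two compliance measures will appear in the report and must be clearly labelled.
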